with either an open, laparoscopic, or robot-assisted laparoscopic approach. **The expected enrollment rate is 2 patients/month.**

Patients diagnosed with primary HCC classified as stage 0 (very early) or stage A (early) will be considered for inclusion in this study. Tumors will be staged preoperatively with computed tomography (CT) and/or magnetic resonance imaging (MRI). Laparoscopic ultrasound will be performed intraoperatively.

Eligible patients will meet the following inclusion criteria:

- Male or female patients aged ≥ 18 and ≤ 75 years
- Primary diagnosis of HCC according to the guidelines published by the American Association for the Study of Liver Diseases (AASLD)²⁸ and the diagnostic criteria used by the European Association for the Study of the Liver (EASL)²⁹:
 - Two imaging techniques showing typical features of HCC; or
 - Cytologic/histologic diagnosis of HCC; or
 - Radiographic classification as LIRAD 5 (Appendix III), regardless of AFP level.
- HCC classification of stage 0 (very early) or stage A (early) according to BCLC staging system criteria (Appendix I):
 - Solitary HCC lesion < 3 cm in diameter
 - ≤ 3 HCC lesions, each ≤ 3.0 cm in diameter
- Total bilirubin level, with or without portal hypertension, less than or equal to 3.0.
- Adequate clinical condition to undergo laparoscopic or robot-assisted laparoscopic TAE and/or MWA as treatment for HCC
- Willing and able to give informed consent

Patients meeting the inclusion criteria will be subjected also to the following exclusion criteria:

- Radiologic (CT or MRI) evidence of invasion into major portal/hepatic venous branches and no extrahepatic metastases (LR-5V or LR-M radiologic classifications)
- Evidence of residual disease at first post-MWA CT examination
- Body Mass Index (BMI) > 35
- Previous history of hepatic resections
- Severe renal dysfunction (creatinine clearance of < 40 mL/min)

- Pregnant or nursing women

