According to a computer-generated variable size blocked randomization method, eligible patients will be allocated on a 1:1 basis to receive the experimental therapy (MWA + TAE) and standard therapy (MWA alone), respectively. The nature of the treatments and their possible adverse effects preclude the use of double-blind and double dummy techniques. In patients randomized to receive the experimental therapy, TAE treatments will be initiated within one week of randomization, then followed by MWA within 4 to 6 weeks after reviewing radiological scans from TAE. MWA will be performed 4 to 6 weeks following randomization in MWA standard therapy groups. Treatment may be discontinued if any exclusion criteria develop in the patient or at the patient's request.

Sample Size

Power calculations are based upon expected 2-year survival rates. The main endpoint is 2-year intrahepatic disease-free survival, measured from the time of randomization which is measured from time of randomization and is defined as the absence of local or regional recurrence of HCC as determined by diagnostic imaging. Considering an estimated 80% and 90% intrahepatic disease-free survival at 2 years of follow-up for patients receiving MWA alone and MWA + TAE combination therapy, respectively, a sample size of 92 patients is required to detect a clinically meaningful 10% absolute difference in 2-year peritoneal disease-free survival with MWA + TAE with a minimum of 95% power and a 2-sided $\alpha = .05$. To account for a 5–10% withdrawal rate (following intraoperative detection of vascular invasion or extrahepatic metastasis, etc.), a sample size of 100 patients is required (50 patients per arm). If the rate of patient enrollment is suboptimal, a covariate adaptive randomization method will be used to allocate patients in a 2:1 ratio to receive experimental therapy (MWA + TAE) and standard therapy (MWA alone), respectively, which would result in an overall sample size of 83 patients.

Clinical Procedures

Preprocedural Strategy

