Patients alive at the time of analysis will be censored at the last follow-up examination or at liver transplantation. Univariate analyses will be performed using the log-rank test of equality for categorical variables and the chi-square test with Cox proportional hazard model for continuous variables to identify clinical variables (Child–Pugh class, Okuda class, Model for End-Stage Liver Disease (MELD) score, etiology of cirrhosis), tumor factors (extrahepatic disease, multicentric disease, tumor size, Milan criteria, AJCC tumor stage, AFP level), and treatment-related factors (TAE, complications, recurrence) predicting intrahepatic disease-free and overall survival. Survival and disease-free survival will be estimated using the Kaplan–Meier method and tested with the log-rank test following the intention-to-treat principle. Statistical analysis will be performed using SAS software (SAS Institute, Cary, NC, USA).

The analysis will be planned at a median follow-up of two years, with an interim analysis scheduled for 1 year after the first patient is enrolled or when 50% of total expected enrollment has been reached.

To improve patient selection in the future, additional exploratory analyses will be performed to identify potential prognostic factors. Table 1 details variables that will be included in a Cox proportional hazards regression model to obtain hazard ratios and 95% confidence intervals (CIs). All P values will be two-sided and a p value $< .05$ will be considered significant.

ETHICAL AND SAFETY CONSIDERATIONS

Protection of Patients

The techniques and procedures used in this study protocol are not investigational or provisional in nature; rather, they are established in the provision of care for patients of the HPB Division at Carolinas Medical Center. The therapeutic benefit of combination of TAE/MWA treatment in this patient population remains unknown and is the focus of this study. The additive risk for adverse events is expected to be equal to the individual risks of the study procedures in this protocol.

Standard Division-specific guidelines will be closely followed to ensure patient safety and clinical well-being during all procedures. Patients will be closely monitored for complications associated with MWA and TAE, including wound complications, hematologic toxicities, and others.

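### 92 patients give about 27–29% power for 80% versus 90% at 2 years, not the stated 95%; the 83-patient 2:1 fallback gives about 22–26%

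*Combined protocol and SAP*

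**What the plan says.** All the design inputs are in the Sample Size section. The assumed rates are given as "Considering an estimated 80% and 90% intrahepatic disease-free survival at 2 years of follow-up", for MWA alone and MWA + TAE respectively. From these the section concludes that "a sample size of 92 patients is required to detect a clinically meaningful 10% absolute difference in 2-year peritoneal disease-free survival", "with a minimum of 95% power" and a two-sided alpha of .05. The endpoint in that sentence is called peritoneal, although it is defined as intrahepatic everywhere else.

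The number is then raised to 100 (50 per arm) to allow for 5–10% withdrawal. If enrolment is slow, allocation switches to 2:1 in favour of the combination, "which would result in an overall sample size of 83 patients". No formula, event target or software is given for any of these numbers.

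The Statistical Analysis section says that disease-free survival will be "tested with the log-rank test following the intention-to-treat principle". On timing it says: "The analysis will be planned at a median follow-up of two years". The Patient Eligibility and Allocation section adds: "The expected enrollment rate is 2 patients/month".

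**The concern.** A 10-point difference between two high survival rates is a small effect for a trial of this size. With 46 patients per arm, only about 14 recurrences are expected by two years, too few for any standard test to reach 95% power. The fallback also goes the wrong way: unequal allocation needs more patients than 1:1 for the same power, yet the total falls from 100 to 83.

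This paragraph is the only justification for the size of the trial, on its primary endpoint. The Objective section words the primary hypothesis as one of no difference between arms. A non-significant result could therefore be read as support for that hypothesis, and readers who trust a 95% power statement would have reason to read it so. At the true power it would show very little.

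**Working it through.** **Inputs.** From Sample Size: p1 = .80, p2 = .90, two-sided alpha .05 (z = 1.960), power 95% (z = 1.645), 92 or 100 patients at 1:1, and 83 at 2:1 (taken as 28 control, 55 experimental). From Statistical Analysis: log-rank test, median follow-up two years. From Patient Eligibility and Allocation: 2 patients per month.

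**Attempt to reproduce 92 patients.** Two-proportion formulas (pooled, unpooled, arcsine, continuity-corrected), exact tests, Schoenfeld, Freedman, single-arm formulas and non-inferiority with a 10-point margin were tried. None gives 92 patients at 95% power. One-sided testing raises power with 92 patients only to about 38–40%. The nearest match is a number of events: HR = ln(.90)/ln(.80) = 0.4722, |ln HR| = 0.7504, and 4(1.960 + 1.645)²/0.7504² = 92.3 events.

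**Patients needed for 95% power.**
- Two proportions, 1:1: (1.960·√(2 × .85 × .15) + 1.645·√(.16 + .09))²/.10² = (0.990 + 0.822)²/.01 = 328.4, so 329 per arm, 658 in total.
- Schoenfeld, 1:1: 92.3 events / .15 average event probability = 616 patients.
- Freedman, 1:1: 102 events / .15 = 680 patients.
- Two proportions, 2:1: 244 control + 488 experimental = 732 patients.
- Schoenfeld, 2:1: (1.960 + 1.645)²/(0.7504² × 2/9) = 103.8 events; divided by .1333, 779 patients.

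**Power at 46 per arm.**
- Two proportions: SE under the null = √(.85 × .15 × 2/46) = 0.0745; SE under the alternative = √((.16 + .09)/46) = 0.0737. z = (0.10 − 1.960 × 0.0745)/0.0737 = −0.62, so power is 26.7%.
- Schoenfeld: expected events = 46 × .20 + 46 × .10 = 13.8. z = √(13.8/4) × 0.7504 − 1.960 = −0.566, so power is 28.6%.

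**All three sizes, 24 months of follow-up for everyone.**

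| Method | 46/46 | 50/50 | 55 vs 28 |
|---|---|---|---|
| Expected events | 13.8 | 15.0 | 11.1 |
| Two proportions, pooled | 26.7% | 28.6% | 26.1% |
| Exact power of chi-square test | 28.1% | 30.3% | 24.3% |
| Schoenfeld | 28.6% | 30.6% | 21.7% |
| Simulated log-rank (20,000 runs) | about 27% | about 29% | 25–26% |
| Fisher's exact test | 18.4% | 19.5% | 20.7% |

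Counting rejections in the wrong direction as well moves the 2:1 figures only to 26.3% (pooled) and 21.8% (Schoenfeld).

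**Effect of analysis timing.** Simulated log-rank power, assuming even entry at 2 per month, constant hazards and no losses:

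| Follow-up | 92 patients | 100 patients |
|---|---|---|
| Median 24 months (as planned) | 25.6% | 27.5% |
| Everyone at least 24 months | 43.6% | 48.1% |
| Everyone at least 60 months | 62.5% | 68.0% |
| Everyone followed to an event | 94.0% | 95.4% |

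**What 92 patients can detect.** Against 80%, about 80% power needs an experimental rate of about 97% (exact chi-square 80.5%, simulated log-rank 78.6%) to 98% (pooled normal approximation 79.8%).

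**Precision.** The 95% CI half-width for the 2-year difference is 1.96·√(.16/n1 + .09/n2): 14.4 points (46/46), 13.9 (50/50) and 16.8 (28 control, 55 experimental).

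**The case against.** The strongest defence is that 92 is a required number of events, and that a log-rank test gains power as follow-up lengthens. Schoenfeld's formula does give 92.3 events. But the protocol calls the 92 patients, inflates it for withdrawals (92/0.92 = 100) and splits it 50 per arm. With only 13.8 events expected by two years, 92 events would require nearly every patient to recur. Even 60 months of follow-up for everyone, which covers the longest disease-free survival time point listed under Objective, leaves power below 70%. The event-count explanation remains a conjecture; the shortfall does not depend on it.

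Three narrower points have some force:
- The 27–29% and 28–31% ranges assume 24 months of follow-up for every patient. For the log-rank test at a median of two years, the simulated values are about one point lower, 25.6% and 27.5%.
- The protocol does not restate 95% power for the 83-patient fallback, so the criticism there is of an implied claim. The fallback nevertheless sits in the same paragraph, with no derivation and no power of its own.
- The hypothesis of no difference can be read as an ordinary null, since no equivalence margin is given. The risk of misreading a non-significant result is a judgement about readers, not a stated claim of the plan.

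The simulated values also vary by one or two points between runs and should not be read to the decimal.

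**Conclusion.** The concern holds and must be fixed. The required sample size is understated roughly sevenfold (658 against 92), so the choice of method cannot account for it. The comparison at 24 months needs only the protocol's own rates, alpha and allocation; the time-to-event versions add proportional hazards, and the timing scenarios add even accrual, constant hazards and no losses. At every size the plan offers, the confidence interval half-width exceeds the 10-point effect it calls clinically meaningful. A non-significant result would be the most likely outcome even if that effect is real.

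**What to change.** Keep the planned size, delete the statement of at least 95% power, name the calculation method, and replace the sentence with text such as:

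> For 80% versus 90% at 2 years, 92 evaluable patients give about 27–29% power (about 28–31% if all 100 are evaluable) at two-sided alpha .05; the 83-patient 2:1 fallback gives about 22–26%. With 92 patients, about 80% power is available only for a difference of roughly 80% versus 97–98%. The 95% CI half-width for the 2-year difference is about 14 points (about 17 under the fallback), so a non-significant result is inconclusive and is not evidence of no difference.

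If the power is quoted specifically for the log-rank test at a median follow-up of two years, give about 26% for 92 patients and about 28% for 100, with the accrual and hazard assumptions. In the same edit, change peritoneal to intrahepatic.

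The cost is a rewording of one paragraph, including its last sentence on the fallback, and a much less favourable stated power. Restoring 95% by enrolment is not realistic at the stated single-centre rate: 658/2 = 329 months, against 100/2 = 50 months for the planned trial. The sponsor could instead change the target effect or design, or add centres, but the 95% statement has to be corrected in any case.

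### The 100 patients said to allow for 5–10% withdrawal keep the stated 92 only up to 8%; at 10% they leave 90

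*Combined protocol and SAP*

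**What the plan says.** All the figures are in the Sample Size section of the combined protocol and SAP.

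- Planning rates: "Considering an estimated 80% and 90% intrahepatic disease-free survival at 2 years of follow-up" for MWA alone and MWA + TAE respectively, with at least 95% power at a two-sided 5% level.
- Number before withdrawals: "a sample size of 92 patients is required".
- Allowance: "To account for a 5–10% withdrawal rate", with the example "following intraoperative detection of vascular invasion or extrahepatic metastasis, etc".
- Number after the allowance: "a sample size of 100 patients is required (50 patients per arm").

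Allocation is 1:1 (Patient Eligibility and Allocation), so 92 means 46 per arm. The plan does not say which rate within 5–10% produced 100, or which inflation formula was used. The Statistical Analysis section specifies Kaplan–Meier estimates and a log-rank test by intention to treat.

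**The concern.** When a plan names a range of withdrawal rates and then a total that accounts for it, a reader will normally take the total to hold at the top of the range. Here it does not: losing 10% of 100 leaves fewer patients than the plan has just called required. No other section repairs this.

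What is at stake is the accuracy of a stated design property. The trial's conduct does not depend on 2 patients. But the plan claims protection up to 10% and delivers it up to 8%, and the unstated method gives no guide for redoing the step if the base number changes.

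**Working it through.** **Inputs** (Sample Size section): base N = 92 (46 per arm); withdrawal d = 5% to 10%; stated total 100 (50 per arm).

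**1. Reproducing the plan's figure.** Enrolment needed to keep N after a fraction d is lost is N/(1 − d). At d = 8% this gives 92/0.92 = 100 exactly, or 46/0.92 = 50 per arm. So 100 can be reproduced, but only as the figure for 8%.

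**2. Across the stated range.**

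| Withdrawal | Remaining from 100 | Enrolment needed for 92 |
|---|---|---|
| 5% | 95 | 92/0.95 = 96.8 → 97 |
| 7.5% (midpoint) | 92.5 | 92/0.925 = 99.5 → 100 |
| 8% | 92 | 92/0.92 = 100 |
| 9% | 91 | 92/0.91 = 101.1 → 102 |
| 10% | 90 | 92/0.90 = 102.2 → 103 |

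With equal arms, 10% needs 46/0.90 = 51.1, so 52 per arm and 104 in total. The largest rate covered is 1 − 92/100 = 8%.

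**3. A more lenient formula.** Multiplying by (1 + d), which under-inflates, gives 92 × 1.10 = 101.2 at 10%. That also exceeds 100, so the choice of formula does not explain the gap.

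**4. What the gap costs.** Use the plan's 80% and 90% and a two-sided 5% test of two proportions, and assume every evaluable patient has a known 2-year status. With n per arm, the pooled proportion is 0.85, and

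power = Φ{[0.10·√n − 1.96·√(2 × 0.85 × 0.15)] / √(0.8 × 0.2 + 0.9 × 0.1)} = Φ{[0.10·√n − 0.990] / 0.5}.

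The 95% half-width for the difference is 1.96 × √(0.25/n).

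| Evaluable | n per arm | Power | Half-width |
|---|---|---|---|
| 95 (5% lost) | 47.5 | 27.4% | ±14.2 points |
| 92 (8% lost) | 46 | 26.7% | ±14.4 points |
| 90 (10% lost) | 45 | 26.2% | ±14.6 points |

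Falling from 92 to 90 costs about 0.5 percentage points of power.

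**5. The base figure.** The same table shows that 92 patients do not give 95% power for 80% versus 90%. The number needed is [(1.960 × 0.505 + 1.645 × 0.5)/0.10]² = 328.4, so 329 per arm or 658 in total. This is a separate error. It matters here only because the withdrawal sentence must not be rewritten in a way that endorses 92.

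**The case against.** Three arguments on the other side have weight.

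*The total fits the range.* Dividing by (1 − d) over 5–10% gives 97 to 103, and 100 lies inside that interval. It also covers the 7.5% midpoint, with 92.5 remaining. The plan never says that 100 protects against the worst case, and it may simply be a round figure for an approximate range. This stands as far as it goes. A reader might infer that the inflation step cannot be reproduced, or that the whole upper half of the range is uncovered; neither is supported. The step is exact at 8%, and only the stretch from 8% to 10% is uncovered, 2 of the 5 percentage points. What remains is that the sentence names 10% and the total does not deliver it.

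*Intention to treat.* Withdrawals after an intraoperative finding occur after randomization, since MWA follows it by weeks. Under the Statistical Analysis section these patients may stay in the analysis, with some or all of their follow-up. This is a proper qualification: 90 remaining is the count if every withdrawn patient is lost. But going from 92 to 100 makes sense only if loss of that kind is expected, so the plan's own reasoning carries the assumption.

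*The point is small beside the base figure.* This is correct. A reader might infer that raising enrolment to 103 or 104 would secure the planned power. It would not: at 46 per arm power is about 27%. Correcting the withdrawal step alone could even make the section look checked when its power claim still fails.

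**Conclusion.** The point holds and is minor. On the plan's own numbers, 100 patients keep 92 only up to 8% withdrawal, and the part of the stated range above 8% is not covered. At 10% the shortfall is 2 evaluable patients (90 against 92), equivalent to 3 enrolled patients, or 4 with equal arms.

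The conclusion rests on two assumptions: that withdrawn patients are lost to the analysis, as the allowance implies, and that the allowance is meant to hold at the upper end of the range. If withdrawn patients are followed and analysed by intention to treat, the shortfall shrinks or disappears. The arithmetic takes 92 as given only to test the step from 92 to 100; it does not support 92 as the number needed for 95% power.

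**What to change.** Restate the allowance so that it matches the total: 100 enrolled leave 95 evaluable patients at 5% withdrawal and 90 at 10%, with 92 kept only up to 8%. Quote power or precision at both ends. On the plan's rates and the assumptions above, that is a 95% half-width of ±14.2 to ±14.6 percentage points, and power of 27.4% to 26.2%. Say also whether withdrawn patients stay in follow-up for the intention-to-treat analysis. The new sentence should describe what 100 patients provide and should not call 92 a valid requirement for 95% power.

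When the base figure is corrected, choose one withdrawal rate, state it, and divide by (1 − d). For example, 658 at 10% gives 658/0.90 = 731.1, so 732 in total (366 per arm). Carrying over the present ratio would give 658 × 100/92 = 715.2, so 716, which is 16 fewer.

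Restating the allowance costs one short edit to the Sample Size section. It asks for no extra patients and no change to design or conduct; the only loss is that the stated allowance reads slightly less favourably.

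### If allocation moves from 1:1 to 2:1 during accrual, the primary log-rank test needs a stratum for allocation period, and the plan names none

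*Combined protocol and SAP*

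**What the plan says.** The Patient Eligibility and Allocation section sets the starting scheme: "According to a computer-generated variable size blocked randomization method, eligible patients will be allocated on a 1:1 basis". It names no stratification factor and expects 2 patients per month.

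The Sample Size section adds the contingency: "If the rate of patient enrollment is suboptimal, a covariate adaptive randomization method will be used to allocate patients in a 2:1 ratio", experimental to standard, "which would result in an overall sample size of 83 patients". It does not define suboptimal enrolment, name the covariates, or say who decides and on what information.

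The Statistical Analysis section gives the comparison of arms: "Survival and disease-free survival will be estimated using the Kaplan–Meier method and tested with the log-rank test following the intention-to-treat principle". It mentions neither allocation period nor calendar time, and it does not say how patients allocated under the two ratios are to be combined. The Cox model in the same section is exploratory. Its covariates come from Table 1, which lists the surgeon and many patient and tumour variables but no enrolment date or allocation period.

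**The concern.** Within a period of constant allocation ratio, randomisation makes the arms comparable. Across two periods with different ratios it does not, unless the analysis compares like with like inside each period. After a move to 2:1, late patients make up more of the combination arm than of the control arm. If late patients do better or worse for reasons unrelated to treatment, part of that difference appears as a treatment effect.

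Accrual is long enough for such a change to be possible. At 2 per month, 83 patients take 83/2 = 41.5 months, and enrolment slow enough to trigger the switch would average less than 2 per month. Surgeon mix, referral pattern and the balance of CT and MRI could all move over that time. At stake is a small directional bias in the primary comparison, which one line of analysis text would remove.

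**Working it through.** **The plan's own figure.** The documents give no figure for bias or drift. The one related figure is the 83-patient total, and it does not follow from the ratio. The variance of a two-arm contrast scales with 1/[share × (1 − share)], so matching the information in 92 patients at 1:1 takes 92 × 0.25/(2/9) = 103.5 patients at 2:1, not fewer. That is a separate problem. Here 83 is taken as given.

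**Inputs from the documents.** Ratio 1:1, then 2:1 (Patient Eligibility and Allocation; Sample Size); 83 patients in total; target difference 10 points, 80% versus 90% (Sample Size).

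**Assumptions.** No treatment effect. The switch comes after n₁ = 24, 40 or 50 patients. (24 is one year at 2 per month and 50 is half of 100. These match the two interim-analysis triggers but are used only as a range.) The gap between the period means of 2-year disease-free survival is 5, 10 or 15 points.

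**Formulae.**
- Combination arm = n₁/2 + (83 − n₁) × 2/3; control arm = n₁/2 + (83 − n₁)/3.
- Late share of an arm = its patients enrolled after the switch ÷ its total.
- Spurious difference = gap × (late share, combination − late share, control).

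For n₁ = 40: combination arm 20 + 28.7 = 48.7, late share 28.7/48.7 = 58.9%; control arm 20 + 14.3 = 34.3, late share 14.3/34.3 = 41.7%; difference 17.2 points.

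| Switch after | Arms | Late shares | Difference in shares | Gap 5 | Gap 10 | Gap 15 |
|---|---|---|---|---|---|---|
| 24 | 51.3 / 31.7 | 76.6% / 62.1% | 14.5 points | 0.73 | 1.45 | 2.18 |
| 40 | 48.7 / 34.3 | 58.9% / 41.7% | 17.2 points | 0.86 | 1.72 | 2.57 |
| 50 | 47.0 / 36.0 | 46.8% / 30.6% | 16.3 points | 0.81 | 1.63 | 2.44 |

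**Upper bound.** With f the fraction enrolled after the switch, the late shares are 4f/(3 + f) and 2f/(3 − f), and their difference is 6f(1 − f)/(9 − f²). This peaks at f = 9 − √72 ≈ 0.515 with value 3 − 2√2 ≈ 0.172. Whenever the switch comes, at most about 17% of the gap passes through.

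**Against sampling error.** With arms of 49 and 34 and disease-free survival near 85%, the standard error of the difference is √[0.85 × 0.15 × (1/49 + 1/34)] ≈ 8 points. A bias of 1.7 points is about 0.2 standard errors.

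**Error rates.** These come from simulation with no treatment effect: 42 patients at 1:1 then 41 at 2:1, exponential times, 2 years of follow-up, a step change between periods, 20,000 trials per row.

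| 2-year survival, early → late | Pooled, two-sided | Stratified by period, two-sided | Pooled, favouring MWA + TAE (nominal 2.5%) |
|---|---|---|---|
| 80% → 80% | 4.6% | 4.9% | 2.5% |
| 80% → 90% | 5.0% | 4.8% | 3.8% |
| 75% → 90% | 5.5% | 4.9% | 4.5% |
| 70% → 90% | 5.8% | 4.9% | 5.0% |

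With a true 80% versus 90% effect and no drift (10,000 trials), power was 24.7% pooled and 25.2% stratified. That difference is about the size of simulation error, so stratifying cost nothing measurable.

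**The case against.** The strongest reply is that two things must happen before there is any bias: the contingency must be used, and outcomes must drift. The documents show neither. They describe surgeons with extensive experience, procedures already established at the centre, and fixed equipment, so a learning curve is speculative. If drift is linear over steady accrual, the gap between period means is only half the total drift wherever the switch falls. A 10-point drift over the whole of accrual is then a 5-point gap, or 0.7–0.9 spurious points. All of this stands and limits the size of the point.

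A second reply is that covariate-adaptive allocation and the Table 1 Cox model already deal with surgeon and case mix. This stands only in part. The adaptive covariates are unnamed, balancing patient factors does not balance calendar period, and the Cox model is exploratory and contains no period term.

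Three stronger readings are tempting.
- A reader might infer that calendar drift as a whole becomes a treatment difference, or that a quarter of the target effect could be artefact. The first is excluded by the 17% bound. The second needs a 15-point gap between periods, for which the documents offer no evidence.
- A reader might suppose that allocation after the switch would be steeper than 2:1, to bring all 83 patients to 2:1 overall. After 40 at 1:1 that would need about 35.3 against 7.7 of the remaining 43. The late shares would be 64% and 28%, and a 10-point gap would give about 3.6 points. The text gives 2:1 as the ratio at which patients are allocated and describes no catch-up.
- A reader might conclude that the switch should be deleted, or that every secondary comparison needs stratifying. Stratifying the survival comparisons deals with the bias described here, and the switch is the only response to slow enrolment that the plan states.

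**Conclusion.** The point holds as a conditional and modest flaw. The plan permits a change of ratio during accrual and names no allocation-period stratum in the test that compares the arms. That the test is unstratified is read from this silence; the plan does not say so outright.

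If the switch is used and outcomes differ between periods, a pooled test is biased by at most about 17% of the gap: about 1.5–1.7 points for a 10-point gap, against a 10-point target. The main inferential effect is directional. With a 10-point improvement over time, overall two-sided error stays near 5% but shifts towards false positives for MWA + TAE (about 3.8% against 2.5%). Worsening outcomes would push the other way.

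These figures rest on 83 patients, the assumed switch points and gaps, and, for the error rates, a step change with complete 2-year follow-up. Drift of this size would not by itself produce the planned effect.

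**What to change.** Add to the Statistical Analysis section: if the allocation ratio is changed, the primary log-rank test, and any Cox estimate of the treatment effect on intrahepatic disease-free or overall survival, will be stratified by allocation period (before or after the switch).

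Add to the Sample Size section: the decision to change the ratio will rest on enrolment counts alone and be made without arm-level outcome data. The trial is open-label and has an interim analysis at 1 year or 50% enrolment, so this should be written down even though the stated trigger is enrolment and not outcome.

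The cost is two sentences and one stratification factor already known for every patient. If there is no drift, the loss of precision is negligible.

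### The Sample Size section's own inputs need about 615–674 patients at 1:1, not 92; the 2:1 fallback of 83 inherits the fault and gives about 22–27% power

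*Combined protocol and SAP*

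**What the plan says.** The Sample Size section opens with its planning rates: "Considering an estimated 80% and 90% intrahepatic disease-free survival at 2 years of follow-up" for MWA alone and MWA + TAE respectively. From these it states that "a sample size of 92 patients is required to detect a clinically meaningful 10% absolute difference", "with a minimum of 95% power and a 2-sided" alpha of .05. It then allows for 5–10% withdrawal: "a sample size of 100 patients is required (50 patients per arm").

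The fallback follows in the same paragraph. "If the rate of patient enrollment is suboptimal", then "a covariate adaptive randomization method will be used to allocate patients in a 2:1 ratio", "which would result in an overall sample size of 83 patients". No formula is shown for 92 or 83. No other effect, alpha or power is given for the 2:1 design. The paragraph does not say whether 83 includes the withdrawal allowance, or what rate counts as slow. The section on eligibility and allocation says: "The expected enrollment rate is 2 patients/month".

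The Statistical Analysis section tests disease-free survival with the log-rank test by intention to treat, at a median follow-up of two years.

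**The concern.** With 10% and 20% of patients having an event by two years, 92 patients yield about 14 events. That is very few for 95% power, even against a hazard ratio near one half. A change to 2:1 normally keeps the required total about the same or raises it, so a smaller total after the change also needs an explanation.

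What is at stake is how the result will be read. The primary hypothesis is worded as no difference between arms. If readers believe the trial had 95% power, a non-significant result will look like evidence of equivalence. With the stated numbers, a true 10-point benefit would be missed about seven times in ten at 92 or 100 patients, and about three times in four at 83.

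**Working it through.** **Inputs (Sample Size section).** Two-year event probabilities 0.20 (control) and 0.10 (experimental); two-sided .05; power .95; allocation ratio k = 1 or 2 (experimental to control). Exponential event times are assumed for the conversion to a hazard ratio.

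- HR = ln(.9)/ln(.8) = 0.472; (ln HR)² = 0.563
- (1.960 + 1.645)² = 12.995
- Mean event probability: 0.150 at 1:1; (2 × 0.10 + 0.20)/3 = 0.1333 at 2:1

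**Step 1. Try to reproduce 92 and 83.**

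*Schoenfeld*, events = 12.995/[p(1−p)(ln HR)²], where p is the share in one arm:
- 1:1: 12.995/(0.25 × 0.563) = 92.3 events; /0.150 = 615 patients
- 2:1: 12.995/(0.2222 × 0.563) = 103.8 events; /0.1333 = 779 patients

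*Freedman*, events = 12.995 × (1 + k·HR)²/[k(1 − HR)²]:
- 1:1: 101.1 events; 674 patients
- 2:1: 88.2 events; 661 patients

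*Pooled two proportions*, n in control = [1.960√(p̄(1−p̄)(1+1/k)) + 1.645√(.16 + .09/k)]²/0.10²:
- 1:1: 328.4 per arm; 657 patients
- 2:1: 243.6 control; 731 patients

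The unpooled formula gives 650 at 1:1 and 799 at 2:1. With a continuity correction the pooled formula gives 698 and 777. None includes withdrawals.

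The figure 92 appears only as the Schoenfeld event count at 1:1. The figure 83 does not appear as a patient count in any variant. Lower power does not rescue it: 2:1 needs 535–630 patients at 90% and 399–470 at 80% (Freedman to Schoenfeld).

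**Step 2. Does the ratio explain the fall?** In patients, going from 1:1 to 2:1 changes the total from 615 to 779 (Schoenfeld), 657 to 731 (pooled) or 674 to 661 (Freedman, about −2%). The plan's falls are 92 to 83 (−10%) and 100 to 83 (−17%).

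**Step 3. What the stated sizes deliver.** Power is by Schoenfeld, Freedman, exact enumeration of the pooled chi-square test, and simulated log-rank (exponential times, complete 2-year follow-up, 100,000 runs). Half-width of the 95% CI for the 2-year difference = 1.96√(.16/n_control + .09/n_experimental).

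| Experimental/control | Events by 2 years | Schoenfeld | Freedman | Chi-square | Log-rank | Half-width (points) |
|---|---|---|---|---|---|---|
| 46/46 | 13.8 | 28.6% | 26.5% | 28.1% | 26.9% | 14.4 |
| 50/50 | 15.0 | 30.6% | 28.4% | 30.3% | 28.7% | 13.9 |
| 55/28 (2:1 throughout) | 11.1 | 21.8% | 24.8% | 24.3% | 25.7% | 16.8 |
| 47/36 (switch after 50) | 11.9 | 24.9% | 25.1% | 26.8% | 26.2% | 15.6 |
| 42/41 (near-equal arms) | 12.4 | 26.1% | 24.4% | 24.1% | 24.8% | 15.2 |

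The switch after 50 patients is illustrative (25 + 22 = 47 experimental, 25 + 11 = 36 control); the plan gives no switch point. The 42/41 row is the limit with no switch.

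If 83 includes 10% withdrawals, about 75 are evaluable (83 × 0.90 = 74.7). Power is then about 20–25% and the half-width runs from 16.0 (38/37) to 17.7 points (50/25).

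**The case against.** **83 may be only an accrual limit.** The plan uses the language of requirement for 92 and 100 only. It makes 83 conditional on slow enrollment and attaches no power to it. This stands: a reader might infer that the plan claims 95% power at 83, and it does not say so. But the paragraph does not say that 83 is set by accrual either. It presents 83 as the consequence of the ratio, directly after a 95% claim that is never withdrawn.

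**The ratio might explain the fall if the numbers are events.** Freedman's event count drops from 101.1 to 88.2, or 12.8%, which is of the same order as 92 to 83. So the stronger statement, that no ratio change could produce such a fall, is not supported; the point holds for patient counts. Other near matches exist: Schoenfeld at 2:1 with 90% power gives 84.0 events, and 92 × 0.9 = 82.8. Either may be coincidence, and neither makes 83 a valid number of patients.

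**The fallback adds little.** This is right. Most of the shortfall comes from 92/100. A reader might infer that 2:1 itself is costly, but comparing 55/28 with 42/41 it costs about 4 points of power by Schoenfeld and none by the other three methods.

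**The ranges are not bounds.** Also right. At 55/28 Fisher's exact test gives 20.7%, and the unpooled formula at 2:1 gives 21.2%. The conclusion does not depend on the choice.

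**The inputs themselves may be misprinted.** The sentence that states 92 also refers to peritoneal disease-free survival, which is not this trial's endpoint. That is a reason to confirm the inputs before editing; it does not reconcile the figures as printed.

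**Conclusion.** The point holds. With the stated inputs, 92 patients at 1:1 is wrong by a factor of about 6.7 to 7.3 (615/92 to 674/92). Power is about 26–29% with 92 evaluable patients and about 28–31% with 100. The fallback inherits the fault: 2:1 needs about 661–779 patients by the Freedman, pooled and Schoenfeld formulas (about 800 unpooled), and 83 evaluable patients give about 22–27% power, or about 20–25% if 83 includes 10% withdrawals.

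That 92 is a number of events reported as patients is likely from the match with 92.3. It remains an inference, since the plan shows no derivation. The origin of 83 is unknown.

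The figures assume 80% and 90% as stated, exponential event times where a hazard ratio is used, and events counted to two years with complete follow-up. The plan's median follow-up of two years would change the event count somewhat, but not enough to approach 92 or more events from about 100 patients when about 15 are expected.

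**What to change.** First confirm the 80% and 90% inputs and the endpoint named in the paragraph, and supply the derivation of 92 and 83 if one exists. If the inputs stand, edit both sentences together: remove the 95% power claim for 92/100 and the statement that 2:1 results in 83. Changing 83 alone would leave the paragraph inconsistent. Suggested text:

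> With 80% vs 90% 2-year intrahepatic disease-free survival and two-sided alpha .05, 100 evaluable patients at 1:1 give about 28–31% power (92 evaluable: 26–29%) and an expected 95% CI half-width of 13.9 points (14.4). If enrollment is slow, allocation may change to 2:1 and enrollment may end at 83 patients. This size is set by accrual, not by power: with 83 evaluable patients power is about 22–27% and the half-width is between about 15 points (near-equal arms) and 16.8 points (2:1 throughout), and both are worse if 83 includes withdrawals.

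Whether to keep the 2:1 option is the sponsor's choice. If it is kept, state the enrollment rate that triggers it and whether 83 includes the withdrawal allowance.

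**Cost.** No procedure or follow-up changes. The sponsor gives up the 95% power claim and states openly that the trial is small for a 10-point difference. This is a short edit, but it does change the stated justification for the trial. Keeping 95% power would take about 657 patients at 1:1 (pooled formula), which at the expected 2 per month is 657/24, or about 27 years.
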